7.1 BLINDING

Due to the nature of the DMARD treatment it is not practical to blind the participant, the clinical team or the research team to the allocated treatment group. This is because the first DMARD prescribed in the DMARD arm, MTX, is taken on a once-weekly basis and is associated with substantial variation in nausea and fatigue over the week following each administration (40).

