14 ASSESSMENTS/SAMPLES/DATA COLLECTION

14.1 SUBMISSION OF TRIAL DATA

Informed Consent Documents, Serious Adverse Events (SAE), Suspected Unexpected Serious Adverse Reaction (SUSAR) and Participant Questionnaire Booklets will be collected via paper case report forms. CTRU will provide an electronic copy of these forms to be printed and completed by research staff at site and the information sent to CTRU, usually by electronic secure file transfer. All other data collection will be via Remote Data Entry (RDE) on electronic case report forms (eCRFs) managed by the CTRU at the University of Leeds. Access to the live STERLING database will be provided by the CTRU following sites being authorised to open to recruitment; guidance on RDE and completing eCRFs will be provided.

Data must only be completed by personnel authorised to do so by the Principal Investigator, as recorded on the trial-specific Authorised Personnel Log.

Where additional documentation is required by CTRU, for example hospital reports and letters, it is the responsibility of staff at research sites to redact all personal identifiable data prior to sending to CTRU. Such records should only include trial number, initials and date of birth to identify the participant. The exception to this is the participant consent form, where the participant's name and signature must not be redacted.

Participating hospitals will be expected to maintain a file of essential trial documentation (Investigator Site File) that will be provided by CTRU, and where applicable, keep copies of all sites completed paper CRFs for the trial (with the exception of QoL & Healthcare Resource use questionnaires).

14.2 SCHEDULE OF EVENTS.

Not included in this table: on reaching below 5mg prednisolone or equivalent for the first time, a 9am cortisol blood test should be performed (sections 14.6 & 14.8).

Participant Consent	Follow-up schedule (weeks);							Telephone Contact (Weeks)	DMARD monitoring blood tests	Blood Pressure (LEF only)
	Screening	Baseline (0)	12	24	36	48	80	4, 8, , 60, 72	As per local guidelines ††	As per local guidelines ††
Target Visit Window	Max. 6 weeks between Screening and Baseline		-/+ 2 weeks	-/+ 2 weeks	-/+ 2 weeks	-/+ 2 weeks	-/+ 2 weeks			
Written Informed Consent/Witnessed verbal informed consent	x									
Reg and Rand										
Registration	x									
Randomisation		x								
Trial Assessments			12	24	36	48	80			
Eligibility Checks	x	x								
Steroid Use Review		x	x	x	x	x	x	x		

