DMARD Use Review if applicable			x	x	x	x	x	x		
Medical History		x	x	x	x	x	x			
AEs/SAEs review			x	x	x	x	x	x		
Chest X-Ray*	x									
Pregnancy Test	x									
RF [§]	x									
ACPA [§]	x									
U&E	x	x	x	x	x	x	x		x	
FBC	x	x	x	x	x	x	x		x	
Liver Function Test	x	x	x	x	x	x	x		x	
HbA1C		x	x	x	x	x	x			
CRP (Also needed for PMR-AS)	x	x	x	x	x	x	x			
ESR		x	x	x	x	x	x			
Physical Examination	x	x	x	x	x	x	x			
Vital Signs	x	x	x	x	x	x	x			
PMR Activity Score		x	x	x	x	x	x			
(PMR-AS) Number of minutes of morning stiffness		x		x				x		
(PMR-AS) Upper limb elevation / active shoulder abduction		x		x				x		
(PMR-AS) VAS global assessment (physician)		x		x				x		

Steroid Free Remission								x		
------------------------	--	--	--	--	--	--	--	---	--	--

* a report from a chest x-ray performed within the 6 months prior to the screening visit is acceptable to confirm eligibility providing that no evidence of interstitial lung disease or tuberculosis or active.

† As a guide the British Society for Rheumatology DMARD monitoring guidelines recommend FBC, U+E and LFT: every two weeks until on stable dose for six weeks, then monthly for three months and quarterly thereafter. Blood pressure should be measured at the same timepoints as these blood tests.

‡ Providing the results of the prior test are acceptable (see section 13.4.1), a window will be allowed one week either side of the scheduled date during the first six weeks, two weeks either side of the next scheduled date for the next three months and one month either side of the next scheduled date thereafter

§ Rheumatoid factor (RF) and anti-citrullinated peptide antibody (ACPA/anti-CCP) both within local laboratory reference range at or within the 12 months prior to the screening visit

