14.5 BASELINE ASSESSMENTS (WEEK 0)

The baseline assessment should take place for all consenting, registered and eligible participants within 6 weeks of screening. The visit should take place in person. Prior to randomisation the assessments listed below

should be completed and documented on the Baseline Assessments eCRF.

- Participant reported current steroid use
- Relevant medical history
- Urea & Electrolytes (U&E) test
- Full blood count
- Liver function test
- HbA1C test
- CRP test
- ESR test
- Physical examination - MSK system including elevation of upper limbs, joint swelling/tenderness/limitation of movement, and vascular including temporal arteries
- Vital Signs – including, BP, heart rate, temperature
- Weight, hip and waist circumference
- PMR Activity Score (52), requiring:
 - CRP (as stated above).
 - VAS global assessment (physician) (0-10).
 - Number of minutes of morning stiffness.
 - Upper limb elevation / active shoulder abduction (EUL) graded as 0-3.

Participant pain VAS (0-10) (see section 14.10)

In addition, the participant must be given the Participant Baseline Questionnaire Booklet (See section 14.10) to complete before completing the randomisation event on the CTRU 24-hour randomisation system. Persons accessing the randomisation system will be required to confirm that all baseline assessments and questionnaires are complete before randomisation can be completed.

14.6 TELEPHONE ASSESSMENTS WEEK 4, 8, , 60 and 72

Participants will be periodically contacted by the site team via a telephone call to check adherence to the prescribed treatment, collect details of adverse events and any significant changes to medical history or other relevant factors that may affect the administration or dosing of DMARD. For participants in the usual care plus DMARD arm, potential dose escalation will be discussed during the call (see section 13.1.11 for MTX escalation or section 13.2.8).

The data listed below will be collected at this time point.

- Steroid and DMARD use
- (S)AE reporting (including Adverse Events related to glucocorticoid toxicity e.g. infection, diabetes, hypertension and fracture)
- State that DMARD monitoring test results, if applicable, have been reviewed and that the participant is ok to continue ongoing prescribing.
- Whether a 9am cortisol test has been advised and if so the date windows during which it is anticipated that it might be done.

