15.2 OPERATIONAL DEFINITION & REPORTING ADVERSE EVENTS/REACTIONS (AES/ARS)

Information about adverse events/reactions whether volunteered by the participant, discovered by investigator questioning or detected through physical examination, laboratory test or other investigation will be collected and recorded on the relevant Clinical Assessment CRF. All adverse events should be recorded in the participant's medical notes so that they can be followed up if necessary.

This is a randomised controlled trial using treatments with well-known safety profiles already established in the therapy of rheumatological conditions. Although not licensed for PMR, MTX has been shown in clinical practice to be safe and well-tolerated in a PMR population (31). Similarly, in the previous trial by Caporali et al., the main adverse effects that occurred more often in the MTX than placebo arm of the trial was mild gastrointestinal adverse effects. The strategy being tested is DMARD (MTX or LEF) in conjunction with usual care steroid taper, compared to usual care steroid taper alone. The IMPs are defined as the DMARDs, MTX or LEF.

Therefore, the following expected adverse events, related to either tapering of steroid for PMR or to the IMPs, will be reported. It is noted that causality (determination that an Adverse Event is an Adverse Reaction related to a particular IMP) may be difficult to determine since participants will also be receiving other medications, including steroids which should not be stopped abruptly and which can cause many of the adverse events listed below; however, because MTX is administered weekly, assessment of causality may be facilitated by temporality of symptoms in relation to MTX administration

15.2.1 Expected AEs potentially related to tapering of steroid for PMR:

- Diagnosis of adrenal insufficiency – see section 17.2.2
- Diagnosis of giant cell arteritis

15.2.2 Expected AEs/ARs potentially related to MTX:

Please report the following if severity is consistent with **CTCAE grade 2 and above (see Appendix 3)**:

- Clinically significant deranged liver function test values (as judged by the local investigator)
- Clinically significant cytopenia (as judged by the local investigator)
- Depression (diagnosis of depression, or initiation or increase of depression medication)
- Infection (infection requiring treatment with oral, IV or IM antibiotics, or any episode of shingles, or a positive community test for COVID-19)

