15.4 RECORDING AND REPORTING AEs, ARs, SAEs, SARs AND SUSARs

Monitoring for safety events should commence on the date of consent and continue until a minimum of 30 days post last dose of randomised treatment.

AEs and SAEs will be collected on the relevant eCRF and reported to CTRU from the date of consent and continue until a minimum of 30 days post last dose of randomised treatment.

Reporting of ARs, SARs and SUSARs to CTRU should commence on the date of the first IMP dose taken and continue until a minimum of 30 days post last dose of randomised treatment.

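### Adverse events are to be collected from consent, but the first scheduled enquiry is the week 4 call, after open-label allocation, and no baseline grade is taken for the participant-reported events

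*Protocol*

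**What the plan says.** Two parts of the protocol set the start of safety collection.

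- **Section 15.4** starts it at consent: "Monitoring for safety events should commence on the date of consent", and "AEs and SAEs will be collected on the relevant eCRF and reported to CTRU from the date of consent".
- **Section 14.2 (schedule of events)** has a row "AEs/SAEs review" with no mark under screening or baseline. It is marked at weeks 12, 24, 36, 48 and 80 and under telephone contact.

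The section 14.4 screening list has no AE item. Section 14.5 introduces its list with "Prior to randomisation the assessments listed below", and that list has none either. AE reporting first appears in section 14.6, headed "TELEPHONE ASSESSMENTS WEEK 4, 8, , 60 and 72". The schedule allows "Max. 6 weeks between Screening and Baseline", and randomisation takes place at baseline. Section 7.1 states that "it is not practical to blind the participant, the clinical team or the research team to the allocated treatment group".

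Sections 15.2.2 and 15.2.3 list the expected events for methotrexate and leflunomide, reportable at CTCAE grade 2 and above. Section 15.2 warns that causality may be hard to judge because participants also take "steroids which should not be stopped abruptly and which can cause many of the adverse events listed below". Section 16.2.2 makes AEs of special interest over the 18 months after randomisation a safety outcome.

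**The concern.** A site that follows the visit schedule has no scheduled step at which to meet section 15.4 before randomisation. That is an internal contradiction in its own right.

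It also bears on the safety comparison. Many of the listed events are symptoms that the participant reports, and all participants arrive on a drug that the protocol says can cause many of the listed events. If nobody records before allocation whether, say, fatigue is present and at what grade, a complaint raised at week 4 can be sorted into old or new only from memory, by people who know the arm.

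Enquiry after allocation is not identical in the two arms. At the calls, dose escalation is discussed only with DMARD participants (14.6). Methotrexate escalation depends on the absence of intolerable toxicity, with nausea as the example (13.1.11). What is at stake is how clearly the harm of the DMARD can be read when it is weighed against any steroid saving. The primary outcome is not affected.

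**Working it through.** The plan gives no figure on this point, so there is none to reproduce. The check is one sum and a comparison of sections.

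**1. Longest interval from consent to the first scheduled AE enquiry**

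- Screening to baseline: at most 6 weeks (14.2). Section 11.2 sets the same limit between registration and randomisation.
- Baseline to first telephone contact: 4 weeks (14.6). The call lists in the trial summary and section 7.4.1 also begin at week 4.
- Interval = 6 + 4 = 10 weeks, of which the last 4 follow open-label allocation.

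This assumes consent at the screening visit and a call on its target date. It is the gap to the first scheduled question, not to any possible detection.

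**2. Which listed events lack a pre-allocation reference**

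| Type of event in 15.2.2 and 15.2.3 | What exists before randomisation | Exposed? |
|---|---|---|
| Liver tests, cytopenia | Liver function test and full blood count at both screening and baseline | No |
| Depression | Defined by diagnosis, or by starting or increasing medication | No |
| Hypertension (leflunomide list) | Defined by new or increased medication; blood pressure measured at both visits | No |
| Infection | Defined by antibiotic treatment, shingles or a positive COVID-19 test | No |
| Participant-reported symptoms | Unitemised history, examination, PMR-IS; no graded item | Yes |

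The methotrexate list has seven participant-reported items: oral mucositis, nausea, abdominal pain, diarrhoea, hair thinning, headache and fatigue. The leflunomide list repeats these and adds paraesthesia and maculo-papular rash: 7 + 2 = 9 items.

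**3. Whether the existing baseline data can supply the grade**

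- The medical history in 14.5 is described only as relevant history, and its content is not itemised.
- Laboratory tests cannot grade nausea, headache or fatigue. Examination may show a rash or mouth ulcer, but no grading is asked for.
- The PMR-IS is taken at week 0 and includes a steroid side-effect domain, but section 16.2.1.1 scores it as domain means on a 0 to 100 scale, not as CTCAE grades by symptom.
- The general AE definition in 15.1 has no rule on new onset or worsening.

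So the baseline data help to recognise known conditions, but they do not show whether a given symptom was already at the reporting threshold.

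**The case against.** The strongest reply has four parts.

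- **Pre-existing conditions are not invisible.** History, notes, examination, blood tests and the PMR-IS come before randomisation. The telephone call asks about significant changes in medical history, and a clinically qualified person reviews the reported events. This stands, and it narrows the gap to item-level grades for the nine symptoms.
- **Events can surface earlier.** AEs may be volunteered or found on examination or testing, and SAEs go to the trials unit within 24 hours of awareness. Events between consent and randomisation also fall outside the post-randomisation safety outcome. This stands too, but it does not remove the conflict between 14.2 and 15.4.
- **How pre-existing events are counted is ordinary SAP content.** True, and the SAP is not shown. But no SAP rule can recover a grade that was not recorded before allocation; data collection is fixed here.
- **Section 18.3 reports AEs by treatment received and severity and states no test between arms.** This limits the consequence to the reading of descriptive tables.

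A reader might go further and infer that symptoms present at entry are counted as trial events, that the comparison is thereby biased against the DMARD, and that nothing collected could correct it. The documents support none of these. No passage states such a counting rule. The grade 2 threshold excludes milder complaints. Every candidate receives the methotrexate leaflet before consenting (section 10), so the difference in information between arms is only partial. The baseline data above give some means of correction.

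**Conclusion.** The contradiction is real. Section 15.4 requires collection from consent, while 14.2, 14.4 and 14.5 schedule no AE enquiry until week 4, up to about 10 weeks after consent and after allocation is known. The consequence is a possibility, not a demonstrated bias: grade 2 or higher participant-reported symptoms already present at entry could be recorded as post-randomisation events, and perhaps not equally in the two arms.

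The protocol gives no baseline prevalence of these symptoms at grade 2 or above and no reporting fraction by arm, so neither the size nor the direction of any bias can be determined. The 10 weeks rests on consent at screening and a call on its target date. The change is worth making because it is cheap and because the missing record cannot be recovered once a participant has been randomised.

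**What to change.** Reconcile 14.2, 14.4 and 14.5 with 15.4. Mark the AE/SAE row of the schedule at baseline and add a matching item to the 14.5 list, to be completed before randomisation. The review should:

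1. record AEs and SAEs since consent; and
2. go through the participant-reported items of 15.2.2 and 15.2.3, noting presence and CTCAE grade.

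In the post-randomisation safety summary, report items that are new or of higher grade than at baseline separately from those already present.

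The cost is protocol wording, one extra eCRF page and a few minutes per participant at an existing face-to-face visit. Reporting in an open-label trial may still differ by arm for symptoms that are truly new; the change does not remove that.

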14.3 PARTICIPANT QUESTIONNAIRE SCHEDULE

Questionnaires	0	12	24	36	48	60	72	80
PMR-IS	x	x	x	x	x	x	x	x
Pain VAS (Also needed for PMR-AS)	x		x					x
EQ-5D-5L	x	x	x	x	x	x	x	x
Health Resource Use	x	x	x	x	x	x	x	x
Steroid Use	Every 4 weeks from week 4 to week 80							

14.4 SCREENING ASSESSMENTS

Trial screening assessments should take place after written informed consent has been obtained and after registration on the CTRU 24-hour Registration system has been completed. Trial Screening assessments are designed to establish participant eligibility to enter the trial and include the following assessments listed below.

- Physical examination - cardiorespiratory, abdominal, skin, head/eyes/ENT, and screening neurological exam, as well as MSK system including elevation of upper limbs, joint swelling/tenderness/limitation of movement, and vascular including temporal arteries
- Chest X-Ray: a report from a chest x-ray performed within last 6 months prior to the screening visit is acceptable to confirm eligibility providing that no evidence of interstitial lung disease or tuberculosis or active infection.
- Pregnancy test for women of childbearing potential
- Rheumatoid factor (RF) test – result from any test performed within last 12 months prior to the screening visit is acceptable to confirm eligibility.
- Anti-citrullinated peptide antibody (ACPA) test – result from any test performed within last 12 months prior to the screening visit is acceptable to confirm eligibility.
- Urea & Electrolytes (U&E) test
- Full blood count
- Liver function test
- CRP
- Vital Signs – including, BP, heart rate, temperature

Where local guidelines apply stricter suitability criteria than those listed below then the local criteria should be applied. However, the following should be applied as a minimum/maximum acceptable parameter:

- Haemoglobin <10.0 g/dL
- Total white cell count <3.5 x10⁹/L
- Absolute neutrophil count <1.5 x10⁹/L
- Platelet count <100 x10⁹/L
- ALT (alanine aminotransferase) or AST > 2 x upper limit of reference range for the laboratory conducting the test
- eGFR (estimated glomerular filtration rate) <30ml/min

Confirmation that the participant meets all other eligibility criteria can be obtained via a combination of i) review of their medical notes or information provided by their GP as part of the referral process and ii) taking the medical history of the participant at the screening visit.

Following the completion of the trial screening assessments, the Eligibility Checklist eCRF should be completed to confirm participant eligibility. All eligible participants should be invited to attend a baseline assessment visit (week 0). If a participant will not be proceeding to randomisation the reason for not proceeding will be captured on the Eligibility Checklist eCRF and no further visits or data collection should be completed.

14.5 BASELINE ASSESSMENTS (WEEK 0)

The baseline assessment should take place for all consenting, registered and eligible participants within 6 weeks of screening. The visit should take place in person. Prior to randomisation the assessments listed below

should be completed and documented on the Baseline Assessments eCRF.

- Participant reported current steroid use
- Relevant medical history
- Urea & Electrolytes (U&E) test
- Full blood count
- Liver function test
- HbA1C test
- CRP test
- ESR test
- Physical examination - MSK system including elevation of upper limbs, joint swelling/tenderness/limitation of movement, and vascular including temporal arteries
- Vital Signs – including, BP, heart rate, temperature
- Weight, hip and waist circumference
- PMR Activity Score (52), requiring:
 - CRP (as stated above).
 - VAS global assessment (physician) (0-10).
 - Number of minutes of morning stiffness.
 - Upper limb elevation / active shoulder abduction (EUL) graded as 0-3.

Participant pain VAS (0-10) (see section 14.10)

In addition, the participant must be given the Participant Baseline Questionnaire Booklet (See section 14.10) to complete before completing the randomisation event on the CTRU 24-hour randomisation system. Persons accessing the randomisation system will be required to confirm that all baseline assessments and questionnaires are complete before randomisation can be completed.

14.6 TELEPHONE ASSESSMENTS WEEK 4, 8, , 60 and 72

Participants will be periodically contacted by the site team via a telephone call to check adherence to the prescribed treatment, collect details of adverse events and any significant changes to medical history or other relevant factors that may affect the administration or dosing of DMARD. For participants in the usual care plus DMARD arm, potential dose escalation will be discussed during the call (see section 13.1.11 for MTX escalation or section 13.2.8).

The data listed below will be collected at this time point.

- Steroid and DMARD use
- (S)AE reporting (including Adverse Events related to glucocorticoid toxicity e.g. infection, diabetes, hypertension and fracture)
- State that DMARD monitoring test results, if applicable, have been reviewed and that the participant is ok to continue ongoing prescribing.
- Whether a 9am cortisol test has been advised and if so the date windows during which it is anticipated that it might be done.

The current steroid dose being taken by the participant, and the participant's current rate of steroid taper, will be used to determine whether the dose is likely to fall below 5mg prednisolone equivalent before the next scheduled study contact. If so, the participant will be advised of the need for a 9am cortisol blood test to screen for possible adrenal insufficiency. This test will be requested in advance by the site study team and the participant will be advised when they will need to have this test done, and

appropriate advice as to how it should be taken (blood to be drawn at 9am at least 24 hours after the most recent steroid dose).

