7.4 PARTICIPANT FOLLOW-UP SCHEDULE

7.4.1 follow-up visits

In-person follow-up assessments with the research team will be scheduled at 24 weeks post randomisation and 80 weeks post randomisation for all participants from both arms. In addition, site research teams will conduct telephone assessments with participants from both arms at weeks 4, 8, 12, 36, 48, 60 and 72.

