14.7 WEEK 12, 24,36, 48 and WEEK 80 FOLLOW-UP STUDY VISITS

These visits will be conducted in clinic, face to face at 24 and 80 weeks post randomisation. The following data will be collected.

- Steroid and DMARD use
- (S)AE reporting (including Adverse Events related to glucocorticoid toxicity e.g. infection, diabetes, hypertension and fracture)
- Relevant medical history
- Urea & Electrolytes (U&E) test
- Full blood count
- Liver function test
- PMR Activity Score (52), requiring: (week 24 & 80 only)
 - CRP;
 - Physician VAS assessing disease activity;
 - Number of minutes of morning stiffness;
 - Upper limb elevation / active shoulder abduction; (EUL) graded as 0-3
 - Participant pain VAS (0-10) (see section 14.10)
- Weight
- Hip and waist circumference (week 80 only)
- HbA1C test(week 24 & 80 only)

- ESR test
- Physical examination – MSK system including elevation of upper limbs, joint swelling/tenderness/limitation of movement, and vascular including temporal arteries
- Vital Signs – including, BP, heart rate, temperature
- Participant questionnaires (see section 14.10)

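### The 9am cortisol trigger does not clearly cover participants who enter the trial already taking 4mg of prednisolone or less

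*Protocol*

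**What the plan says.** **Trigger.** Three places in the Protocol set it.

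- Section 14.6 (telephone assessments): the current taper rate and dose "will be used to determine whether the dose is likely to fall below 5mg prednisolone equivalent before the next scheduled study contact". When a fall is expected, the participant is told of the need for a 9am cortisol, and "This test will be requested in advance by the site study team".
- Section 14.8: a 9am cortisol is suggested when the dose first drops below 5mg within the trial period.
- Section 14.2: a note above the schedule of events says the test should be done on first reaching a dose below 5mg, and refers to 14.6 and 14.8.

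**How the test is taken.** Section 14.6 specifies "blood to be drawn at 9am at least 24 hours after the most recent steroid dose".

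**Who can enter.** Section 8.1 requires current steroid treatment for PMR and at least one past relapse. It sets no minimum dose and no limit on how long ago the relapse was. Section 3 says the baseline switch to prednisolone keeps the equivalent dose, rounded up to the nearest 1mg.

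**Where planning is written.** The look-ahead sits under the heading "14.6 TELEPHONE ASSESSMENTS WEEK 4, 8, , 60 and 72". Its data item is "Whether a 9am cortisol test has been advised and if so the date windows during which it is anticipated that it might be done". Section 14.5 (baseline) and section 14.7 (headed "14.7 WEEK 12, 24,36, 48 and WEEK 80 FOLLOW-UP STUDY VISITS") record steroid use but contain no cortisol item.

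**What the result feeds.** Section 16.2.2 defines the adrenal insufficiency outcome from a low 9am cortisol, or an intermediate value followed by a positive short synacthen test. Section 18.3 reports the proportion in both groups.

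**The concern.** The trigger is written as a crossing of 5mg. Someone already on the low side at entry has nothing to cross, unless the dose first rises to 5mg or more and then comes down again.

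These people are in the group the screen is meant for. Section 5.3 says that 5mg daily or more for four weeks or more can cause adrenal insufficiency that may last months to a year or more after the dose goes below 5mg. Section 5.2 gives a usual starting dose of 15-25mg, so a participant now on 4mg or less will normally have had that exposure.

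Two things are at stake. One is safety: an at-risk participant may continue tapering without the test. The other is case ascertainment: the outcome depends on the test result, so an untested participant can hardly be counted as a case.

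A smaller point concerns planning. The draw needs a fixed hour and a 24-hour gap from the last dose, yet the step that plans it is attached to the calls only.

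**Working it through.** The Protocol states no figure on this point, so there is none to reproduce. The check sets the texts side by side.

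**1. Can a participant start below 5mg?** The inputs are the entry dose d (no minimum, section 8.1) and rounding up to the nearest 1mg (section 3).

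- d of 4mg or less: the trial dose is 4mg or less, below the threshold.
- d above 4mg and up to 5mg: the trial dose is 5mg, at the threshold, so the next 1mg step is a crossing.
- d above 5mg: the trial dose is 6mg or more, so a later crossing triggers the test normally.

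Only the first group is affected.

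**2. Does any trigger reach that group?**

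| Section | Event described | Entrant at 4mg or less |
|---|---|---|
| 14.6 | dose likely to *fall* below 5mg before the next contact | Not met: already below |
| 14.8 | dose *drops* below 5mg for the first time in the trial period | Not met, unless the dose first rises to 5mg or more |
| 14.2 | first *reaching* a dose below 5mg | Ambiguous: arguably reached before the trial |
| 14.5 | baseline assessments | No cortisol item |

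On 14.6 and 14.8, such a participant would be tested only after an increase followed by a new fall, so testing would hinge on a later dose increase such as one for relapse.

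**3. How large is the effect?** No entry-dose distribution is given, so the number affected cannot be calculated. For scale only: 200 participants at 1:1 is 100 per arm. If all randomised participants form the denominator (an assumption), each undetected case lowers that arm's proportion by 1/100, or one percentage point. The minimisation factor that splits dose at 5mg does not help, because it is the dose before the last relapse and not the dose at entry.

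**4. Which contacts carry the planning step?** Contacts before week 80 are weeks 0, 4, 8, 12, 24, 36, 48, 60 and 72, nine in all.

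- Section 14 schedule: the step is at weeks 4, 8, 60 and 72. It is absent at weeks 0, 12, 24, 36 and 48, so 5 of 9 contacts lack it.
- Section 7.4.1 schedule, under which "site research teams will conduct telephone assessments with participants from both arms at weeks 4, 8, 12, 36, 48, 60 and 72": the step is absent at weeks 0 and 24, so 2 of 9 lack it.

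The two counts differ because the Protocol conflicts over weeks 12, 36 and 48. Section 7.4.1 and the trial-design row of section 3 make them calls. The follow-up row of section 3, section 14.2 and the heading of 14.7 make them visits. The text of 14.7 adds to the doubt: "These visits will be conducted in clinic, face to face at 24 and 80 weeks post randomisation". Baseline and week 24 lack the step on either reading.

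**The case against.** The strongest reply is that the screen is not missing. Sections 14.2 and 14.8 trigger it by event, for every participant, whatever the type of contact. The site runs the taper (7.2) and its rheumatologist prescribes it (12.6). Steroid use is reviewed at every contact from baseline. Section 14.8 expects the draw at a local pathology clinic, so it can be arranged at short notice once the dose has dropped. All of this stands, and it reduces the missing look-ahead to a planning gap.

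A reader might infer something stronger from the schedule. On the section 14 reading, look-ahead covers weeks 4-8, 8-12, 60-72 and 72-80, which is 4 + 4 + 12 + 8 = 28 weeks. That leaves 80 - 28 = 52 weeks (65%) without it, including an unbroken 48 weeks from week 12 to week 60. The Protocol does not support calling this a gap in screening. Those weeks lack one planning sentence; they do not lack the trigger or dose review, and the 48 weeks open with a visit at week 12 and contain visits at weeks 24, 36 and 48. The count also includes time after a participant's first drop, when no look-ahead is needed. On the 7.4.1 call list it shrinks to weeks 0-4 and 24-36, or 16 of 80 weeks (20%).

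On low-dose entrants, the reply is that 14.2 can be read to include them, that their number may be small, and that diagnosed adrenal insufficiency is in any case a reportable adverse event (15.2.1). The first point is fair as a possible reading, but a safety trigger should not depend on which of three verbs a site follows. The second cannot be checked. The third gives a clinical backstop and does not replace the test on which 16.2.2 bases the outcome.

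It is also fair that *suggested* in 14.8 may reflect intended clinical discretion. Its difference in strength from 14.2 and 16.2.2 is a secondary wording point.

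**Conclusion.** The concern holds for participants who enter at 4mg or less. Eligibility and the baseline switch permit them, 14.6 and 14.8 do not clearly cover them, and 14.2 is at best ambiguous. A site following the text may not test them, and the adrenal insufficiency proportion may be undercounted as a result.

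The size is unknown. The finding rests on the wording of the trigger and on there being no minimum entry dose; it assumes nothing about how many such people will be recruited. It does not show that they will never be screened: a site may read 14.2 broadly, may order the test on its own judgement, or may meet the 14.8 wording after a later rise and fall in dose. Nor does it bear on the primary outcome.

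The absence of the look-ahead from baseline and the visits is a minor planning gap. The call-or-visit conflict at weeks 12, 36 and 48 is a separate inconsistency.

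**What to change.** **Main change.** State in 14.8 that a participant already below 5mg prednisolone-equivalent at baseline has a 9am cortisol at or soon after entry, with the same data recorded as for any other 14.8 test. Match the note in 14.2. The cost is one sentence and a few extra blood tests of a type already in the Protocol.

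**Minor addition.** Copy the 14.6 look-ahead, advance request and data item into 14.5 and into the week 12, 24, 36 and 48 visits in 14.7. This costs wording and one eCRF item at contacts that already review steroid use.

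**Separate correction.** Decide whether weeks 12, 36 and 48 are calls or visits. If visits, bring 7.4.1, the section 3 trial-design row and the opening sentence of 14.7 into line with 14.2. The strength of the instruction in 14.8 can be settled in the same edit.
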